This study will employ an intra-individual balanced 2 x 18-day in-hospital protocol (experimental insomnia vs. control sleep condition, see **Figure 8**). The first 2 nights of each 18-day protocol will be adaptation nights, and the 3rd night will serve as the baseline night, with a sleep opportunity of 8 hours (23pm-7am) on all 3 nights. In the experimental insomnia study arm, insomnia symptoms will be induced during the next 3 nights, followed by 1 night of 8-hour recovery sleep (for more details, see model description under Procedures). During nights with insomnia symptom induction, sleep onset will be delayed by 1 hour (midnight 12am), the sleep period (12-6am) will be disrupted by hourly 20 min long awakenings, and sleep offset will be advanced by 1 hour (6am). This episode of 3 nights of experimental insomnia followed by 1 night of recovery sleep will be repeated three times. After the last experimental insomnia episode, participants will have 4 recovery nights. In the control arm of the study, participants will receive an 8-hour sleep opportunity for all 18 nights of the protocol. These 2 arms of the study will be separated by an interval of at least 1 month in order to allow recovery from blood sampling. Monthly separation was chosen to control for potential effects of menstrual phase in women. Depending on the bed occupancy space, participants will stay in a private room in the CRC. If a private room is not available, participants will stay in a double occupancy room with an individual of the same sex (assigned at birth)

Visit 1. Initial screening. All potential participants will have the study explained to them in detail by the PI or another senior member of the research team. If interested, potential participants will sign the informed consent and nursing staff in the Clinical Research Center (CRC) will take vital signs and collect a blood sample. A short battery of screening tests and questionnaires will also be collected in order to assess health status (see **Appendix 1** for blood tests and questionnaires). Potential participants will then be introduced to the web-based, secured diary recording system (REDCap²²) and given an actigraphy watch to take home to estimate sleep-wake habits, for 2 weeks (see **Appendix 1**). These data will be used to verify nightly sleep duration between 7 to 9 hours to be used for eligibility.

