Visit 2. Medical history, physical, and sleep screening. During this visit, the study physician will meet with the study participant for a physical exam and review of blood test results. Anemia and abnormal thyroid results are the most frequent exclusionary medical findings in our healthy volunteers. Participants who remain eligible following the medical screen will be instrumented for polysomnographic recording (PSG) for a sleep screening night in the CRC, in order to rule out any possible sleep disorders (see detailed exclusion criteria in Protection of Human Subjects).

Visit 3 and 4: Two 18-day in-hospital stays (experimental insomnia and sleep control condition). Throughout the 18-day **experimental insomnia condition** (see **Figure 8**), participants will start with 3 nights of adaptation/baseline nights, before undergoing 3 episodes of 3 nights of insomnia symptom induction followed by 1 night of 8 hours of sleep. Four recovery nights will follow the last experimental insomnia episode. During this 18-day period, participants will have 8 days of intensive recording (on the baseline night, every 2nd and 4th day of each episode, as well as the 3rd recovery night at the end of the protocol, see also **Figure 'Study Protocol'**). These intensive measurement periods will include PSG recordings, blood sampling, and urine collection during daytime (7am-11pm) and nighttime (11pm-7am) periods. Emotional and physical well-being will be assessed on computerized visual analog scales every 4 hours throughout waking periods (see **Appendix 2**) and a pain testing battery will be administered at 2pm (see **Appendix 3**). For the experimental insomnia nights, the sleep opportunity will be from 12am-6am (rather than 11pm-7am) with hourly 20min-awakenings. However, participants will remain in bed in a semi-supine position during the wakeful nighttime periods (11pm-12am, 20-min awakening bouts, 6am-7am), in order to maintain consistent postural and physical activity inputs across all study nights and conditions. Lights

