In case of last-minute cancellations of the 18-day in-hospital stays, we will attempt to fill the open slots with new participants. We will use adaptation day 1 of the study for screening purposes (i.e., initial and medical/overnight screening), and if fulfilling screening criteria, the participant will continue the following day with adaptation day 2 of the study.

Visit 5: Follow-up. Seven to 14 days following their final discharge from the CRC (after completing both study protocols), participants will return to the CRC to have a final blood draw to ensure that any potential activation of the blood markers have returned to baseline and to review their study experience.

Participants.

We anticipate screening 612 subjects in order to have 34 participants with an attrition rate of 32% complete both 18-day in-hospital study protocols. We typically screen 18 potential participants for every one that enters the in-hospital part of the study. In our experience with 2 25-day in-hospital stays separated by a monthly interval, we have an attrition rate of 32%. As such, 34 participants will need to enter the hospital phase to have 26 participants complete 2 18-day in-hospital protocols.

Procedures.

Model of repeated exposure to experimentally-induced insomnia symptoms. The hypothesis will be tested within an experimental insomnia model characterized by (1) induction of insomnia symptoms for 3-day long episodes, and (2) the repeated nature of such insomnia episodes, i.e. after a night of good sleep, the next episode will start. Participants will undergo 3 of those 3-day episodes of insomnia symptom induction, each followed by 1 night of 8 hours of sleep. Such patterns are

commonly experienced in individuals suffering from insomnia, where intervals of 1 to 3 nights of poor sleep are followed by a night of good sleep, likely due to the buildup of sleep pressure during the interval of poor sleep^{31;41}. The advantage of this approach is that it mimics sleep-wake patterns frequently found in the general population for a number of reasons, and in chronic pain populations in particular^{28;39}. In contrast to previous studies, mostly using single episodes of sleep restriction or deprivation, this approach will facilitate the translation of findings directly into clinical applications.

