Polysomnographic recording (PSG). Sleep will be recorded using the Embla system N7000 (Medcare US, Buffalo) on the screening night visit to ensure that participants are free from sleep disorders. The Embla system will also be used to collect sleep data on the 8 intensive recording days of each study run (baseline, every 2nd and 4th night of each episode, 3rd recovery night at end of protocol). The PSG montage will follow standard criteria and sleep EEG will be manually stage-scored on a 30 second epoch basis³. The main purpose for sleep data collection is the quantification and comparison of various sleep indices in insomnia symptoms induction and control nights (e.g., sleep duration, sleep latencies, percent time spend in different sleep stages). For explorative analysis (not specified in aims), spectral analyses will be conducted on EEG data using Remlogic software (Medcare US, Buffalo). The homeostatic response will be calculated for each episode, by calculating change from baseline for the two homeostatic markers N3 (slow wave sleep) and delta power, and comparing between episodes. We will explore whether the robust and stable homeostatic response that has been observed within exposure to a single episode of deficient sleep¹ will increase with episode repetition. Spectral analysis will be performed by the PI, who is experienced in this analysis¹⁹.

Blood Sampling. On the baseline day (Day 3), as well as on the 8 intensive recording days of each 18-day study run, blood samples will be drawn at 1100am and after pain testing, around 1550 (50 min after pain testing) per simple needle stick. The amount of the blood collected at each blood draw will range between 10ml and 50ml. The total amount of blood taken over each 18-day protocol will not exceed 550ml.

IL-6 will be measured in plasma in our laboratory, using a high sensitivity enzyme immunosorbent assay (ELISA, Quantikine ® HS, R&D Systems, Minneapolis, MN). We will measure IL-6 twice throughout the 8 intensive recording periods. IL-6 will be also measured in vitro as the capacity of monocytes to express IL-6. In brief, whole blood will be stimulated with lipopolysaccharide (LPS,

100pg/ml), incubated with fluorescence-conjugated antibodies (CD14, CD45, IL-6), and IL6-positive monocytes will be quantified using flow cytometry (Gallios™ Beckmann-Coulter Inc, Flow Cytometry Core at BIDMC).

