Resolvins are the newly discovered anti-inflammatory lipid mediators that are actively involved in the resolution of inflammation and pain²⁴. Resolvins of the E series are produced from eicosapentaenoic acid (EPA)²³, and possess potent pro-resolving actions that include counter-regulation of cytokines and reduction in pain in animal models³⁵. Resolvins of the E series will be measured in the Lipid Mediator Metabolomics Core at the Brigham and Women's Hospital Boston (Director [name]), using liquid chromatography-mass spectrometry (LC-MS MS). Assessment will be performed twice per intensive recording day at 1100am and after pain testing.

PGE2 metabolite will be measured in collections of nighttime urine (11pm-7am) and daytime urine collected during/after pain testing (2pm-5pm) during the 8 intensive recording days. Urinary PGE2 will be analyzed in our lab using an EIA (Cayman Chemical, Ann Arbor, MI), and levels will be adjusted for urinary creatinine levels.

Creatinine will be measured in night- and daytime urine collects and used for the adjustment of PGE2 levels.

Cyclooxygenase 2 (COX-2), is the enzyme involved in PGE2 synthesis and is the target of the pain-relieving nonsteroidal anti-inflammatory drugs (NSAID)³³. COX-2 will be measured in vitro by the capacity of monocytes to express COX-2 after stimulation with lipopolysaccharide (LPS, 100pg/ml) and incubation with fluorescence-conjugated antibodies (CD14, CD45, COX-2), using flow cytometry (Gallios™ Beckmann-Coulter Inc, Flow Cytometry Core at BIDMC). Though not part of the aims, COX-2 measures may corroborate proposed findings of a role of PGE2 in experimentally-induced insomnia symptoms. COX-2 expression will be measured in the 1100am blood sample obtained on during baseline and on the 8 intensive recording days.

Opioid peptides: Beta-endorphin will be measured in leukocytes using flow cytometry.

Cortisol will be measured in plasma and saliva and assayed in the Harvard Catalyst Central Lab, using the Access Chemiluminescent Immunoassay (Beckman Coulter Fullerton, CA).

Norepinephrine: Norepinephrine will be measured in urine and plasma/serum collects and assayed in the CORE lab on the HPLC system.

DNA/RNA extraction from blood/saliva:

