RNA will be extracted from blood by RNA extraction method using the QIAGEN RLT buffer or another RNA stabilizing reagent. Blood drawn at 1100am during the 4th and 14th days will be used for RNA extraction in the laboratory. Samples will be stored in -80°C freezer for future genetic analyses.

DNA will be extracted from saliva using the saliva DNA isolation kit from Norgen Biotek Corporation (product# RU 45400). Saliva samples obtained from participants at 1100am during baseline and every heavy recording day will be used for DNA extraction in the laboratory. Samples will be stored in -80°C freezer for future genetic analyses.

Cardiovascular markers: Radial artery blood pressure (BP) will be assessed by averaging three to five measurements of BP taken at 3 min intervals following standard American Heart Association (AHA) guidelines and using Dinamap automated oscillometric device (GE Medical SIT Inc., Milwaukee, WI) every 4h through the waking periods of the protocol, as well as during the disruption intervals at night. The arterial waveform in a finger of the non-dominant hand will be derived on a beat-to-beat basis by digital photoplethysmography (Portapres, TPI, Brussels, Belgium). The Portapres system will be used between 0830 and 0930 for autonomic tests on pain testing days.

Autonomic tests: To determine the effects of repeated fragmentation sleeps on autonomic system, participants will undergo valsalva's maneuver (VM) test, fast breathing test and mental stress test on 6 days' mornings. The tests will begin at 0930h, following portapres instrumentation and 3

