Outcome variables will be measured on 8 out of the 18 in-hospital protocols (baseline, 2nd experimental insomnia/control night and 4th recovery night of each episode, and 3rd recovery night at end of protocol). The analysis will focus on episode-wise comparison of outcome variables between experimental insomnia and control sleep conditions. Although several forms of linear mixed model will be used, our main analysis will focus on daily summary measures (mean, max, min, slope, AUC, etc.) The models will be constructed as follows: the study has two within factors (measurements over several days and measurements within the same day). Data will be used as it is or the difference between the two experimental conditions by episode will be used in the analysis. The main method of data analysis will employ linear mixed model (repeated measures analysis).

By defining appropriate contrast we can evaluate (i) the difference between experimental insomnia nights and recovery sleep nights for the entire study period, (ii) the difference between days 3 and 6 (day6 minus day3), 7 and 10, and 11 and 14 separately. We expect that each of the contrasts will yield a significantly positive value. These comparisons will show if IL-6 values drops or increases from experimental insomnia nights to recovery sleep nights. Similarly, from the same model, by defining appropriate contrasts, we will evaluate the difference between days 6 and 7, 10 and 11, and 14. These contrasts are expected to be negative. Time will also be used as a continuous variable to test the trend and quadratic effect, and if the above contrast does not suggest strong episode-wise effect but mild increment (or decrease) from one episode to the next. We may also use piece-wise regression with a knot at each episode (and also with just one knot to capture the effect of prolonged recovery towards the end of the experiment). As mentioned earlier, many of the exploratory analysis will be guided by plots and summary assessment of the data. Other inflammatory marker (PEG2, resolvins) will be analyzed in a similar fashion.

Sensitization variables (HPT, PPT, TS) will be analyzed similarly and are expected to mimic the time course of inflammatory variables. Correlation between inflammatory markers and sensitization variables will be evaluating using the Altman-Bland method². The linear mixed model described above can be used to obtain the necessary estimates to compute this correlation.

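### The day-numbered Aim 1 contrasts use days 6, 10 and 14, which are off the recording schedule, so none of the five fully printed pairs has both days measured

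*Combined protocol and SAP*

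**What the plan says.** **Layout of the stay.** Study Design states: "The first 2 nights of each 18-day protocol will be adaptation nights, and the 3rd night will serve as the baseline night". Three episodes follow, each of three insomnia nights and one recovery night. The stay of 18 nights closes with four recovery nights.

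**When outcomes are recorded.** Visit 3 and 4 lists the baseline night and "every 2nd and 4th day of each episode, as well as the 3rd recovery night at the end of the protocol". The polysomnography paragraph gives the same list by night: "baseline, every 2nd and 4th night of each episode, 3rd recovery night at end of protocol". The opening of Assessment of Aim 1 repeats it by condition: baseline, the second insomnia (or control) night, the fourth (recovery) night of each episode, and the third final recovery night.

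**Aim 1 contrasts.** The same section then specifies "the difference between days 3 and 6 (day6 minus day3), 7 and 10, and 11 and 14 separately", all expected positive. Next come 6 v 7, 10 v 11 and a third contrast that names day 14 without a partner, all expected negative.

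**Aim 3 contrasts.** Assessment of Aim 3 uses 3 v 7, 7 v 11 and 11 v 15, then the mean of days 7, 11 and 15 (called recovery days) against day 17.

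**Clues to the numbering.** Blood Sampling says "On the baseline day (Day 3), as well as on the 8 intensive recording days of each 18-day study run, blood samples will be drawn". The DNA/RNA paragraph says "Blood drawn at 1100am during the 4th and 14th days will be used for RNA extraction in the laboratory". The provision for last-minute cancellations places the overnight screening on adaptation day 1, with adaptation day 2 following.

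**The concern.** The Aim 1 section describes one schedule and then contrasts days that are not on it. Days 6, 10 and 14 recur in both the rise and the fall contrasts, so this is not a single slip. A reader cannot tell from the text whether the schedule or the contrasts should govern.

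These are the episode-wise tests of the trial's central question, namely whether the response grows with repeated exposure. They are written for IL-6, extended to PGE2, resolvins and the three sensitization measures, and carried to Aim 2 by reference to a similar strategy. They therefore reach all eight primary outcomes in Table 2. With day as a category in the mixed model, an unsampled day has no data, so the contrast cannot be computed and another day must be substituted. That substitution should be written down before the data are seen. Otherwise the results may be reported as if they followed three insomnia nights when the recording follows two.

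**Working it through.** **Step 1: rebuild the nights (Study Design).**
- Nights 1-2 are adaptation and night 3 is baseline.
- Insomnia nights are 4-6, 8-10 and 12-14.
- Recovery nights are 7, 11 and 15-18.
- Check: 3 + (3+1) + (3+1) + 3 + 4 = 18. The fourth night of episode 3 is thus also the first of the four final recovery nights.

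**Step 2: reproduce the plan's own count of eight.** Baseline is night 3. The 2nd and 4th nights of the episodes are 5 and 7, 9 and 11, 13 and 15. The third final recovery night is 17. The set is 3, 5, 7, 9, 11, 13, 15, 17, which is eight, as stated.

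**Step 3: test each Aim 1 pair.** Suppose the day label equals the night number plus a constant k. Any two recording days then differ by an even number. The printed pairs differ as follows:
- 6 - 3 = 3
- 10 - 7 = 3
- 14 - 11 = 3
- 7 - 6 = 1
- 11 - 10 = 1

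All five differences are odd, so no value of k puts both days of any pair on the schedule. The sixth pair cannot be tested as printed. If its missing day is 15, as the pattern suggests, 15 - 14 = 1 and it fails too.

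**Step 4: compare the two plausible numberings.**

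| | Night n ends on day n (k = 0) | Daytime n precedes night n, recorded the day after the listed night (k = 1) |
|---|---|---|
| Recording days | 3, 5, 7, 9, 11, 13, 15, 17 | 4, 6, 8, 10, 12, 14, 16, 18 |
| Aim 1 days off schedule | 6, 10, 14 | 3, 7, 11 |
| Printed Aim 1 pairs with both days measured | 0 of 5 | 0 of 5 |
| Aim 3 contrasts with all days measured | 4 of 4 | 0 of 4 |

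**Step 5: decide which numbering the text supports.** Four points favour k = 0:
- Blood Sampling labels the baseline draw Day 3, and baseline is night 3.
- Aim 3 calls days 7, 11 and 15 recovery days.
- Aim 3 sets one recovery night against three and tests this with day 17. Day 17 follows three recovery nights (15, 16, 17) only if night 17 has ended.
- Aim 1 expects a fall from day 6 to day 7, which needs recovery night 7 to come in between.

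Three points do not fit it cleanly:
- RNA blood on days 4 and 14 matches k = 1 (after nights 3 and 13), if those draws belong to recording days, which the text does not say.
- In the cancellation provision, night 1 comes after day 1.
- One Aim 3 sentence treats the day 15 to 17 difference as one between sleep restriction and recovery, although the comparison that follows lists day 15 as recovery.

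**Step 6: exposure behind the labels at k = 0.** Days 6, 10 and 14 follow three insomnia nights (for example 4, 5, 6) and are not recording days. The scheduled days 5, 9 and 13 follow two (for example 4, 5).

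**The case against.** The best defence is that this is a labelling slip with an obvious repair. Each episode has exactly one insomnia recording and one recovery recording, and the Aim 1 section lists them by condition before it numbers any days. An analyst who codes by episode and condition has only one insomnia value per episode to use. The first Aim 1 contrast (insomnia against recovery nights over the whole study) carries no day numbers and can be estimated. Trend and piecewise models in continuous time are also planned and do not need data on days 6, 10 or 14. The schedule figures are not shown and may state the numbering.

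Most of this stands, and it limits the point. It does not remove it, because no figure can make the printed pairs agree with the list of recordings in the same section.

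The defence also disposes of some stronger readings. A reader might infer that Aim 3 is equally broken, or that daytime measures on days 7, 11 and 15 precede recovery sleep. That would need daytime n to come before night n with draws on the listed night's own date. The support for it is a remark on replacement screening and one on stored RNA, while the Aim 3 wording itself points the other way. A reader might also infer that the rise could be measured after either two or three insomnia nights, but no Aim 1 marker or pain test is scheduled after the third.

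**Conclusion.** The point holds for the day-numbered Aim 1 contrasts. None of the five fully printed pairs has both days measured under any single offset, and the third fall contrast lacks its second day. On the best-supported numbering the fault lies in three labels (6, 10 and 14), and the Aim 3 contrasts match the schedule 4 of 4.

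The result rests on the eight recordings being those listed and on one constant offset between night and day numbers. If Blood Sampling is read literally, with Day 3 as an extra draw on top of days 4, 6, ... 18, then 3 v 6 alone becomes available. That reading counts baseline twice, against the other sections.

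Counting the failure as six of six would go beyond the text, since the sixth pair's second day is assumed. Nor do the documents show that no sample was taken after recovery sleep. Power and the target of 26 completers are unaffected. The plan should be corrected, but this is a mismatch between schedule and analysis, not a design failure.

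**What to change.** 1. State that each recording day is the listed night plus the daytime that follows it, with night n ending on day n.
2. Rewrite the Aim 1 contrasts as rise 3 v 5, 7 v 9, 11 v 13 and fall 5 v 7, 9 v 11, 13 v 15. Code them in the model by condition: baseline, second insomnia night and recovery night of each episode.
3. Keep the Aim 3 contrasts as written.
4. Bring the RNA draw days (4 and 14) into line with the stated numbering, or say that they are separate from the recording days.
5. If the study team in fact numbers days so that daytime n precedes night n, move every label up by one. Rise becomes 4 v 6, 8 v 10, 12 v 14. Fall becomes 6 v 8, 10 v 12, 14 v 16. Aim 3 becomes 4 v 8, 8 v 12, 12 v 16, and the mean of 8, 12, 16 v 18.
6. Label any samples already taken by the nights actually slept before them.

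Under the first numbering the cost is wording only. Under the second, daytime measures would move only if they had been planned on the listed night's own date, and the last would fall on day 18, still within the stay. Either way there are no added recording days, draws or participants.
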